1.3.2 Clinical study results

1.3.2.1 Clinical pharmacology studies

In a clinical pharmacology study in Japanese hemodialysis patients (MR13A9-2), plasma MR13A9 concentrations after the first and third intravenous doses showed a biphasic elimination pattern: a rapid initial phase and a slow elimination phase. After the first dose, C_{max} was 4.38 ± 1.31 and 8.95 ± 2.24 ng/mL and $AUC_{0-\infty}$ was 97.38 ± 35.02 and 240.05 ± 87.23 hr•ng/mL in the 0.5 and 1 µg/kg groups, respectively. After the third dose, C_{max} was 5.38 ± 1.84 and 8.69 ± 2.45 ng/mL and $AUC_{0-\infty}$ was 151.34 ± 48.55 and 316.85 ± 106.67 hr•ng/mL in the 0.5 and 1 µg/kg groups, respectively, showing increases in C_0 , C_{max} , AUC_{last} , $AUC_{0-\infty}$, and AUC_{0-48} with increasing dose. T_{max} occurred at the first

sampling time, except for 1 patient receiving 0.5 μ g/kg. $t_{1/2}$ was 34.1 to 39.0 hours after the first dose and 40.0 to 49.3 hours after the third dose. The accumulation ratio of Day 5 to Day 1 calculated using the C_{max} , $AUC_{0.48}$, and trough values indicated a low likelihood of accumulation of MR13A9.

In a clinical pharmacology study in healthy Japanese subjects (MR13A9-1), the cumulative urinary excretion rate became almost constant by 36 hours after the initial dose (i.e., 15 hours after the final dose). The cumulative urinary excretion rate for up to 72 hours after the initial dose (i.e., 51 hours after the final dose) ranged from 71.6% to 76.8%, being similar across the dose groups (1.0, 3.0, 5.0, 10, 20, and 40 μ g/kg).

In a clinical pharmacology study in non-Japanese hemodialysis patients (CR845-CLIN1003), postdialysis plasma concentrations of MR13A9 decreased by 75% to 80% on average down below 2 ng/mL on average in all treatment groups (1, 3, and 6 μ g/kg). These results suggested that unchanged MR13A9 is eliminated primarily through the kidneys.

1.3.2.2 Efficacy and safety

In a Japanese phase II clinical study (MR13A9-3), 105 previously treated hemodialysis patients with pruritus received intravenous doses of MR13A9 0.25, 0.5, 1.0, or 1.5 µg/kg, or placebo 3 times weekly for 2 weeks. With respect to efficacy, the primary endpoint of change in VAS (i.e., change based on the larger VAS value either in the morning or the evening during the 7 days, the latter half of the treatment period) (mean \pm standard deviation) was 23.4 ± 20.0 mm, 28.0 ± 18.2 mm, 32.8 ± 25.4 mm, and 41.2 ± 22.8 mm in the 0.25, 0.5, 1.0, and 1.5 μ g/kg groups, respectively, versus 26.4 \pm 22.3 mm in the placebo group. These results suggested a dose-dependent improvement by treatment with MR13A9 at doses $\geq 0.5 \,\mu g/kg$. With respect to safety, the incidence of adverse drug reactions was 23.8% (5/21 subjects), 33.3% (7/21 subjects), 61.9% (13/21 subjects), 47.4% (9/19 subjects), and 82.6% (19/23 subjects) in the placebo, 0.25, 0.5, 1.0, and 1.5 µg/kg groups, respectively. Commonly reported adverse drug reactions (in ≥ 10% of subjects in any of the MR13A9 groups) included blood thyroid stimulating hormone decreased, dizziness, blood prolactin increased, nausea, feeling abnormal, and somnolence. The incidence of these adverse drug reactions was as follows: blood thyroid stimulating hormone decreased, 9.5% (2/21 subjects) in the 0.25 µg/kg group, 31.6% (6/19 subjects) in the 1.0 µg/kg group, and 30.4% (7/23 subjects) in the 1.5 μ g/kg group; dizziness, 4.8% (1/21 subjects) in the 0.25 μ g/kg group, 9.5% (2/21 subjects) in the $0.5 \mu g/kg$ group, 10.5% (2/19 subjects) in the $1.0 \mu g/kg$ group, and 17.4% (4/23 subjects) in the 1.5 µg/kg group; blood prolactin increased, 4.8% (1/21 subjects) in the $0.25 \mu g/kg$ group, 4.8% (1/21 subjects) in the $0.5 \mu g/kg$ group, 5.3% (1/19 subjects) in the $1.0 \,\mu g/kg$ group, and 17.4% (4/23 subjects) in the $1.5 \,\mu g/kg$ group; nausea, 4.8% (1/21 subjects) in the 0.25 μg/kg group and 17.4% (4/23 subjects) in the 1.5 μg/kg group; feeling abnormal, 4.8% (1/21 subjects) in the 0.5 µg/kg group and 17.4% (4/23 subjects) in the 1.5 µg/kg group; and somnolence, 4.8% (1/21 subjects) in the 0.25 µg/kg group, 4.8% (1/21 subjects) in the 0.5 µg/kg group, and 13.0% (3/23 subjects) in the 1.5 µg/kg group.

Reported serious adverse events included the following: 2 events (encephalopathy and shunt stenosis) in 2 subjects in the 0.25 μ g/kg group, 8 events (abdominal distension, influenza, diverticulitis, dizziness, hyperglycaemia, cholecystitis, hypotension, and muscular weakness) in 4 subjects in the 0.5 μ g/kg group, and 1 event (dizziness) in 1 subject in the 1.5 μ g/kg group. Of these events, relationship to study treatment was not ruled out for 4 events (diverticulitis, dizziness, hypotension, and hyperglycaemia) in 3 subjects in the 0.5 μ g/kg group and 1 event (dizziness) in 1 subject in the 1.5 μ g/kg group. Study treatment was discontinued or interrupted due to 1 event in 1 subject in the 0.25 μ g/kg group, 2 events in

2 subjects in the 0.5 μ g/kg group, 1 event in 1 subject in the 1.0 μ g/kg group, and 17 events in 10 subjects in the 1.5 μ g/kg group. Dependency was assessed as being present in 2 subjects in the placebo group and 1 subject in the MR13A9 0.5 μ g/kg group.

In a non-Japanese phase II clinical study (CR845-CLIN2005 Part B), 65 hemodialysis patients with moderate to severe pruritus received intravenous doses of MR13A9 1.0 μ g/kg or placebo 3 times weekly for 2 weeks. With respect to efficacy, the primary endpoint of change in VAS (i.e., change from baseline in the mean VAS for the most intense itching at Week 2) (mean \pm standard deviation) was -33.1 ± 23.03 mm in the 1.0 μ g/kg group versus -21.5 ± 24.79 mm in the placebo group. With respect to safety, the incidence of adverse drug reactions was 9.4% (3/32 subjects) in the placebo group and 18.2% (6/33 subjects) in the 1.0 μ g/kg group. Commonly reported adverse drug reactions (in \geq 5% of subjects in the MR13A9 group) included dizziness, hypoaesthesia, and pruritus.

In a non-Japanese phase II clinical study (CR845-CLIN2101), 174 hemodialysis patients with moderate to severe pruritus received intravenous doses of MR13A9 0.5, 1.0, or 1.5 µg/kg, or placebo 3 times weekly for 8 weeks. With respect to efficacy, the primary endpoint of change in NRS (i.e., change from baseline in the mean itch NRS at Week 8) (mean \pm standard deviation) was -3.9 ± 2.48 , -2.8 ± 2.24 , and -3.3 ± 2.18 in the 0.5, 1.0, and 1.5 µg/kg groups, respectively, versus -1.9 ± 2.29 mm in the placebo group. With respect to safety, the incidence of adverse drug reactions was 2.2% (1/45 subjects), 27.3% (12/44 subjects), 26.8% (11/41 subjects), and 22.7% (10/44 subjects) in the placebo, 0.5, 1.0, and 1.5 µg/kg groups, respectively. Commonly reported adverse drug reactions (in \geq 5% of subjects in any of the MR13A9 groups) included dizziness, somnolence, headache, paraesthesia, fatigue, and hyperglycaemia.

1.4 Summary of Expected Adverse Drug Reactions and Benefits

1.4.1 Expected adverse drug reactions

In a phase II clinical study in Japanese hemodialysis patients (MR13A9-3), 84 subjects received intravenous doses of MR13A9 0.25, 0.5, 1.0, or 1.5 $\mu g/kg$ 3 times weekly for 2 weeks. Adverse drug reactions reported in $\geq 10\%$ of subjects in any of the MR13A9 groups included blood thyroid stimulating hormone decreased, dizziness, blood prolactin increased, nausea, feeling abnormal, and somnolence. Although adverse drug reactions suggesting the effects of MR13A9 on the central nervous system tended to occur relatively frequently, most of them were mild and none of them were severe in severity.

In a phase II clinical study in non-Japanese hemodialysis patients (CR845-CLIN2005 Part B), 33 subjects received intravenous doses of MR13A9 1.0 μ g/kg 3 times weekly for 2 weeks. Adverse drug reactions reported in \geq 5% of subjects receiving MR13A9 included dizziness and hypoaesthesia. In a phase II clinical study in non-Japanese hemodialysis patients (CR845-CLIN2101), 129 subjects received intravenous doses of MR13A9 0.5, 1.0, or 1.5 μ g/kg 3 times weekly for 8 weeks. Adverse drug reactions reported in \geq 5% of subjects in any of the MR13A9 groups included dizziness, somnolence, headache, paraesthesia, fatigue, and hyperglycaemia.

In non-Japanese clinical studies, an adverse event of serum sodium increased associated with the aquaretic effect of KOR agonists¹³⁾ was reported in subjects receiving ≥ 5 µg/kg. In addition, an adverse event of tachycardia associated with the same effect was reported. In a phase I clinical study in healthy Japanese adult males (MR13A9-1), blood sodium increased was reported in 4 of 6 subjects in the 5.0 µg/kg group during the repeated-dose period. These

events were reported only in clinical studies in subjects with normal renal function and have not been reported in clinical studies in hemodialysis patients.

1.4.2 Expected benefits

The Japanese and non-Japanese phase II clinical studies in hemodialysis patients with pruritus have suggested the efficacy of MR13A9 for pruritus in hemodialysis patients. Treatment with MR13A9 is also expected to relieve pruritus in hemodialysis patients in the present study.

2. Study Title and Development Phase

2.1 Title of Study

A phase II clinical study of MR13A9 in previously treated hemodialysis patients with pruritus (Protocol No.: MR13A9-4)

2.2 Development Phase

Phase II

3. Study Objectives

To determine the dose-response relationship for the efficacy, safety, and pharmacokinetics of MR13A9 0.25, 0.5, or 1.0 μ g/kg administered to previously treated hemodialysis patients with pruritus for 8 weeks in a placebo-controlled, double-blind design.

3.1 Endpoints for Efficacy

3.1.1 Efficacy endpoints

- 1) Primary endpoint
 - Itch NRS score (The primary variable is change from baseline in the mean NRS score at Week 8 of the treatment period)

The degree of the most intense itching within a day will be assessed using NRS scores.

- 2) Secondary endpoints
 - Itch score based on the Shiratori's severity criteria¹⁴⁾
 - Skindex-16 score¹⁵⁾
 - 5-D itch scale score¹⁶⁾
 - Patient Global Impression of Change (PGIC)

3.1.2 Rationale for the efficacy endpoints

1) Primary endpoint

The itch NRS score has been selected as the primary endpoint because it is used widely as a pruritus assessment method in clinical studies²⁾ and is also used as the primary endpoint of the non-Japanese phase III clinical study.

- 2) Secondary endpoints
 - The Shiratori's severity criteria have been selected as an endpoint for pruritus, provided that they are used widely to assess the degree of itching by dermatologists in Japan and that they can also be used to assess sleep disorder because they use the effects on daily activities as the criteria for severity.
 - Skindex-16 and 5-D itch scale have been selected as QOL endpoints for pruritus because they are used to assess the skin disease-related QOL.
 - PGIC has been selected as an endpoint for treatment effects assessed by subjects.

3.2 Endpoints for Safety

3.2.1 Safety endpoints

- Occurrence of adverse events
- Occurrence of adverse drug reactions
- Occurrence of adverse events of special interest
- Laboratory tests (hematology, blood biochemistry, endocrinology)
- Vital signs (blood pressure, pulse rate, body temperature)
- Body weight
- 12-lead electrocardiography (ECG)
- Dependency assessment

3.2.2 Rationale for the safety endpoints

In addition to the endpoints generally used for safety evaluation, endocrinology testing and dependency assessment have been selected because these endpoints could be affected by opioids. In addition, for careful assessment of their effects on the central nervous system, adverse events of special interest have been established.

3.3 Endpoints for Pharmacokinetics

3.3.1 Pharmacokinetic endpoint

• Plasma concentration of MR13A9 (unchanged drug)

3.3.2 Rationale for the pharmacokinetic endpoint

This endpoint has been established to determine the pharmacokinetic dose-response relationship in Japanese hemodialysis patients with pruritus.

4. Study Population

This study will enroll previously treated hemodialysis patients with pruritus who meet all of the inclusion criteria and none of the exclusion criteria below.

4.1 Inclusion Criteria

4.1.1 Inclusion criteria

- 1) Patients aged 20 years or older (at the time of signing informed consent)
- 2) Japanese patients providing written informed consent for study participation in person (Their first- and second-degree relatives must be all Japanese)
- 3) Patients with chronic renal failure on periodic hemodialysis (HD, off-line HDF, on-line HDF, or I-HDF) 3 times weekly for ≥ 12 weeks prior to the informed consent procedure who can continue hemodialysis without changing its frequency or method (excluding temporary changes with no changes in treatment strategies) during the study
- 4) Patients whose pruritus treatment for 1 year prior to the informed consent procedure

meets either (1) or (2) below:

(1) Drug therapy with nalfurafine hydrochloride for ≥ 2 consecutive weeks

- (2) Inadequate response to both drug therapies a) and b) below:
 - a) Systemic (e.g., oral, injection) therapy with antihistamines or antiallergics contained in prescription drugs indicated for the treatment of itching for ≥ 2 consecutive weeks
 - b) Local (topical) therapy with prescription drugs indicated for the treatment of itching or moisturizers prescribed by physicians
- 5) Patients not receiving nalfurafine hydrochloride for ≥ 2 weeks prior to the start of the screening period
- 6) Patients whose pruritus has been treated with 1 or more drugs listed below since prior to the start of the screening period:
 - Drugs indicated for the treatment of itching (prescription/nonprescription) (excluding nalfurafine hydrochloride)
 - Moisturizing drugs (prescription/nonprescription)
 - Products formulated with either of the above
- 7) Patients whose NRS score in the 7 days prior to the start of the treatment period (including the score recorded on the day at Week 0) meets both of the below:
 - NRS scores have been recorded for ≥ 5 days.
 - The mean value of the recorded scores exceeds 4.
- 8) Patients whose itch score based on the Shiratori's severity criteria in the 7 days prior to the start of the treatment period (including the score recorded on the day at Week 0) meets both of the below:
 - Itch scores during the day and the night have been recorded for ≥ 5 days.
 - The larger itch score either during the day or the night is "3. Moderate itching" or greater for ≥ 2 days.
- 9) Patients who can record the symptom diary, as instructed by the principal investigator, subinvestigator, or clinical research coordinator

4.1.2 Rationale for the inclusion criteria

- 1) To include patients old enough to provide consent in person legally.
- 2) To comply with the ethical principles that have their origin in the Declaration of Helsinki and GCP.
- 3) To include patients on stable hemodialysis.
- To include patients whose pruritus has been treated with drug therapy and who have had an inadequate response to the drug therapy other than nalfurafine hydrochloride. Patients previously treated with nalfurafine hydrochloride will be included because it is assumed that they have not responded to drugs other than nalfurafine hydrochloride.
- 5) To exclude the effects of nalfurafine hydrochloride on the efficacy and safety of MR13A9.

6)-8) To include patients who have a certain degree of itching continuously.

9) To include patients who can perform appropriate assessment using a symptom diary.

4.2 Exclusion Criteria

4.2.1 Exclusion criteria

- 1) Patients with itching caused by conditions other than chronic renal failure or complications of chronic renal failure, which could affect the efficacy evaluation in the opinion of the principal investigator or subinvestigator (e.g., atopic dermatitis, chronic urticaria)
- 2) Patients with concurrent hepatic cirrhosis
- 3) Patients who received phototherapy to treat itching within 4 weeks prior to the start of the screening period
- 4) Patients who previously received any study drug (including placebo) in a clinical study of MR13A9
- 5) Patients with any concurrent or previous disease that could affect the evaluations in this study in the opinion of the principal investigator or subinvestigator
- 6) Patients with any adverse drug reaction to nalfurafine hydrochloride in the past who are ineligible for study participation in the opinion of the principal investigator or subinvestigator
- 7) Patients with drug hypersensitivity to opioids
- 8) Patients whose laboratory data at the start of the screening period meet any of the criteria (1) to (3) below:
 - (1) ALT > 2.5 times the upper limit of normal
 - (2) AST > 2.5 times the upper limit of normal
 - (3) Total bilirubin > 2 times the upper limit of normal
- 9) Patients whose dry weight is < 24 kg at the start of the screening period
- 10) Patients with congestive heart failure (NYHA functional class IV) (Appendix 1)
- 11) Patients with concurrent malignancy or a history of malignancy within 5 years prior to the informed consent procedure
- 12) Patients with concurrent or previous drug abuse (defined as illicit drug use)
- 13) Patients with concurrent or previous alcoholism
- 14) Patients with a history of severe drug hypersensitivity
- 15) Patients with mental disorder (i.e., depression, schizophrenia, or dementia) that could affect the evaluation of the investigational product
- 16) Female patients who are pregnant, breastfeeding, intending to become pregnant between the informed consent procedure and the end of the follow-up period, or unwilling to use appropriate methods to prevent conception
- 17) Male patients who are unwilling to use appropriate methods to prevent conception between the start of study treatment and 12 weeks after the day of the final dose

18) Patients who received treatment with any study drug or medical device in a clinical study (including clinical studies of medical devices) within 12 weeks prior to the informed consent procedure, or who are planning to participate in another clinical study before the end of the follow-up period of this study

- 19) Patients scheduled to be hospitalized to receive any medical intervention between the informed consent procedure and the end of the follow-up period
- 20) Patients withdrawn from the study in the screening period because they are found not meeting either of inclusion criteria 7) or 8) after participation in the study
- 21) Patients withdrawn from the study in the screening period after re-registration
- 22) Other patients ineligible for study participation in the opinion of the principal investigator or subinvestigator

4.2.2 Rationale for the exclusion criteria

1)	-5	To perform the efficacy evaluation of MR13A9 appropriately.
-,	- /	

6)-8), 10)-14), 19),	To ensure the safety of subjects.
----------------------	-----------------------------------

22)

9) To prevent the dose of the investigational product from exceeding the prespecified dose.

To exclude the effect of this condition on protocol adherence.

To ensure the safety of pregnant women, fetuses, and infants because the safety of MR13A9 in them has not been established.

To establish a certain time interval for subjects, between administration of another study drug and administration of MR13A9 because it is impossible to rule out the possibility of an interaction between these drugs and the development of delayed adverse reactions of another investigational product as well as it is necessary to do so from the ethical aspect.

20), 21) Re-registration will not be permitted because it could affect the efficacy evaluation.

4.3 Discontinuation of Individual Subjects

4.3.1 Discontinuation criteria (discontinuation of individual subjects)

- 1) Adverse event (The name of the adverse event should be recorded in the case report form):
 - It is necessary to withdraw the subject from the study because of the adverse event in the opinion of the principal investigator or subinvestigator
 - The subject does not want to continue the study due to the adverse event
- 2) Lack of efficacy (inadequate response):
 - Study continuation may cause an unacceptable risk to the subject because of the lack of efficacy of the study drug in the opinion of the principal investigator or subinvestigator
- 3) Voluntary request for study discontinuation by the subject (Discontinuation due to an adverse event is categorized as 1) above and discontinuation due to the lack of efficacy is

categorized as 2) above)

4) Significant protocol deviation during the study

- Any GCP violation is found
- After registration, the subject is found not meeting any of the inclusion criteria or meeting any of the exclusion criteria stipulated in the protocol
- Study continuation may cause injury to the subject because of the subject's protocol noncompliance in the opinion of the principal investigator or subinvestigator
- 5) Four consecutive missed doses of the study drug
- 6) Pregnancy
- 7) Discontinuation of the entire study
- 8) Discontinuation of the study at the study site
- 9) Lost to observation or follow-up
 - Study continuation becomes impossible because of failure to contact the subject
- 10) Any other cases where it is necessary to withdraw the subject from the study in the opinion of the principal investigator or subinvestigator (A detailed reason should be recorded in the case report form)

4.3.2 Responses to the discontinuation of any individual subject

If a subject meets any of the criteria described in "4.3.1 Discontinuation criteria (discontinuation of individual subjects)" during the study, the principal investigator or subinvestigator will immediately decide to discontinue the study. On the day of dialysis after the decision to discontinue, the prespecified assessment items at discontinuation will be measured and assessed and the date of discontinuation and the reason for discontinuation will be recorded in the case report form. The date of discontinuation will be the day when the principal investigator or subinvestigator decides to discontinue the study.

If the study is discontinued because of the occurrence of an adverse event, the principal investigator or subinvestigator will promptly provide appropriate treatment for the subject and perform a follow-up investigation, as instructed in "9.12.9 Follow-up investigation"

If the study is discontinued during the treatment period, the next day of the assessments at discontinuation will be regarded as the start date of the follow-up period.

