7.2.2 Treatment period

In addition to the use of restricted concomitant medications (e.g., anti-itch drugs) used at the start of the screening period, the study drug will be injected into the venous line of the dialysis circuit at the end of each dialysis session for 8 weeks (3 times weekly, 24 times in total). The injected volume of the study drug will be determined based on the subject's dry weight on the day of dosing according to Table 7.2.2-1. If any dialysis circuit trouble precludes injection through the dialysis circuit, it will be permissible to administer the study drug as an intravenous injection. If a fourth dialysis session is extraordinarily required within the week, the study drug will be administered (up to 4 times weekly). If only the extracorporeal ultrafiltration method is used, the study drug will not be administered. Details are stipulated in a separate procedure.

Table 7.2.2-1 Doses

			MR13A	9 dose	
Dry weight	Injected volume	0.25 μg/kg	0.5 μg/kg	1.0 μg/kg	Placebo
		group	group	group	group
< 45.0 kg	0.35 mL	8.75 μg	17.5 μg	35.0 μg	0 μg
\geq 45.0 kg, $<$ 65.0 kg	0.50 mL	12.50 μg	25.0 μg	50.0 μg	0 μg
\geq 65.0 kg, $<$ 85.0 kg	0.70 mL	17.50 μg	35.0 μg	70.0 μg	0 μg
≥ 85.0 kg	0.85 mL	21.25 μg	42.5 μg	85.0 μg	0 μg

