7.2.3 Follow-up period

A 2-week period after the end of the treatment period or the assessments at discontinuation in the treatment period is defined as the follow-up period, during which subjects will receive no study drug. Subjects will continuously use any restricted concomitant medications (e.g., anti-itch drugs) used at the start of the screening period.

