9.12.1.1 Adverse event collection period

Adverse events will be collected between the time of signing informed consent and the final visit in the follow-up period.

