13.6.1 Adverse events and adverse drug reactions

Analysis will include events occurring between the start of study treatment and the end of the follow-up period. Analysis of adverse drug reactions will be similar to adverse events.

1) Incidence of adverse events and adverse drug reactions

The number of events, the number of subjects experiencing events, the incidence of events and its two-sided 95% confidence interval will be presented. Fisher's exact test will be used for comparisons between the placebo group and each of the MR13A9 0.25, 0.5, and 1.0 μ g/kg groups. The between-group difference in the incidence of events and its two-sided 95% confidence interval will be presented.

2) Incidences of adverse events and adverse drug reactions (serious events and events led to discontinuation)

The numbers of events, the numbers of subjects experiencing events, and the incidences of events will be presented for all events, events led to death, serious events other than death, and events led to discontinuation.

3) Occurrence of adverse events and adverse drug reactions

The number of subjects experiencing events and the incidence of events will be presented for all events and by primary SOC and PT.

4) Occurrence of adverse events and adverse drug reactions (by severity)

The numbers of events by severity will be presented for all events and by primary SOC and PT.

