12.1.1 Incidence of adverse events and adverse drug reactions

The number of events, the number of subjects experiencing events, the incidence of events and its two-sided 95% confidence interval will be presented. Fisher's exact test will be used for comparisons between the placebo group and each of the MR13A9 0.25, 0.5, and 1.0 μ g/kg groups. The difference in the incidence between the placebo group and the MR13A9 0.25, 0.5, and 1.0 μ g/kg groups and its two-sided 95% confidence interval will be presented.

12.1.2 Incidences of adverse events and adverse drug reactions (serious adverse events, adverse events leading to discontinuation of treatment period, and adverse events of special interest)

For adverse events occurring between the start of study treatment to the end of the follow-up

Protocol No. MR13A9-4 Version: 1.0

period, and adverse events between the start of treatment with the study drug to the end of the treatment period, the number of events, the number of subjects experiencing events, and the incidence of all events, adverse events leading to death, serious adverse events excluding death, events leading to interruption, events leading to discontinuation of the treatment period, and adverse events of special interest will be presented.

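### Adverse events are compared only as crude counts and percentages although early stoppers are observed for less time; rates per time at risk should supplement them

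*Protocol*

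**What the plan says.** **Observation time.** Protocol 9.12.1.1: "Adverse events will be collected between the time of signing informed consent and the final visit in the follow-up period". Protocol 7.2.3 gives completers and early stoppers the same length of follow-up: "A 2-week period after the end of the treatment period or the assessments at discontinuation in the treatment period is defined as the follow-up period". For a subject who stops early, Protocol 4.3.2 adds: "If the study is discontinued during the treatment period, the next day of the assessments at discontinuation will be regarded as the start date" of that period. Protocol 9.12.9 follows existing events to resolution but does not extend the search for new ones.

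**Analysis.** Protocol 13.6.1: "Analysis will include events occurring between the start of study treatment and the end of the follow-up period". SAP 12.1 adds a second window that ends with the treatment period. SAP 12.1.1: "The number of events, the number of subjects experiencing events, the incidence of events and its two-sided 95% confidence interval will be presented", and "Fisher's exact test will be used for comparisons between the placebo group and each of the MR13A9 0.25, 0.5, and 1.0" μg/kg groups, together with a difference in incidence and its 95% CI. SAP 12.1.2, 12.1.3 and 12.1.5 are descriptive. SAP 12.1.4 gives numbers of events by severity. SAP 12.1.5 gives numbers of special-interest events by severity, action taken, outcome and period of resolution.

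Neither document plans a person-time rate, a time-to-event analysis or a cumulative incidence for AEs. Treatment duration is summarised in SAP 9.3 but is not used as a denominator.

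**The concern.** The safety dose-response is part of the study objective (Protocol 3). A crude count or percentage treats a subject watched for four weeks like one watched for ten. If the groups stop early at different rates, the AE comparison mixes the effect of dose with the effect of observation time. Three kinds of output are exposed:

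- event counts, including the severity and special-interest tables, which have no time denominator;
- terms that would have appeared later, other than the one that led to the stop;
- subject incidence, where a subject stops before having any AE. Protocol 4.3.1 lists several such reasons, among them lack of efficacy, voluntary request and four consecutive missed doses.

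The direction is not fixed. More stopping at a high dose would flatter that dose. More stopping on placebo, for instance for lack of efficacy, would make the active doses look worse. Special-interest events are sought by questioning once a week (Protocol 9.12.5), so an early stopper is also asked fewer times.

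**Working it through.** The documents state no figure for the AE comparison, so there is none to reproduce. The power figures in Protocol 7.6.2 concern the itch score.

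**Inputs from the documents:** 8 weeks of treatment and 2 weeks of follow-up for everyone; 60 subjects per group.

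**Assumptions (not in the documents):** share stopping d, week of stop s, ten-week incidence q.

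**1. Time observed.** Completer: 8 + 2 = 10 weeks. Stop at week s: s + 2 weeks, so 4 weeks for a stop at Week 2.

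**2. Stopping unrelated to AEs, constant hazard, s = 2.**

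Crude incidence = (1 − d)·q + d·[1 − (1 − q)^(4/10)].

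Event-count factor = (1 − d) + 0.4·d.

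For q = 0.30 the stopper's term is 1 − 0.70^0.4 = 0.133, so the shortfall is d × 0.167. For q = 0.60 it is 1 − 0.40^0.4 = 0.307, so the shortfall is d × 0.293.

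| d | Crude, q = 30% | Shortfall (points) | Crude, q = 60% | Shortfall (points) | Count factor |
|---|---|---|---|---|---|
| 5% | 29.2% | 0.8 | 58.5% | 1.5 | 0.97 |
| 10% | 28.3% | 1.7 | 57.1% | 2.9 | 0.94 |
| 20% | 26.7% | 3.3 | 54.1% | 5.9 | 0.88 |
| 30% | 25.0% | 5.0 | 51.2% | 8.8 | 0.82 |

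Over q = 30 to 80%, d = 5 to 30% and s = 1 to 6, the shortfall runs from 0.3 to 12.5 points.

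**3. Stops spread evenly over the 8 weeks.** Mean observation is about 4 + 2 = 6 weeks. The count factor is (1 − d) + 0.6·d, which is 0.92 at 20% and 0.98 at 5%.

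**4. AEs clustered early.** Assume 47.4% have an event in the first 2 weeks (the crude adverse drug reaction incidence at 1.0 μg/kg in MR13A9-3, 9/19), then 3% per week. The ten-week figure of 58.8% falls to 57.9% with 10% stopping at Week 2 and to 57.1% with 20%. The losses are 0.8 and 1.7 points, against 2.9 and 5.9 under a constant hazard at q = 60%.

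**5. Stopping caused by the AE itself.** This was simulated with 200,000 subjects per setting, q = 60%, and 10 to 50% of AEs leading to a stop. Any-AE incidence stays at 59.9 to 60.1%. Events per subject fall from 0.92 to between 0.89 and 0.79. Events per subject-week stay at 0.0912 to 0.0916.

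**6. The treatment-period window.** A Week-2 stopper contributes 2 of 8 weeks, so the count factor at 20% stopping is 0.80 + 0.20 × 0.25 = 0.85, against 0.88 in the longer window. The second window does not remove the problem.

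**7. Size against precision.** With 20% stopping in one group and 5% in the other, q = 30% and all stops at Week 2, the risk difference is distorted by 3.3 − 0.8 = 2.5 points. Its 95% half-width is about 1.96 × √(2 × 0.30 × 0.70 / 60) = 0.164, or 16 points.

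**The case against.** A reader might infer that a dose with more early stopping will look safer than it is. The documents do not support that as a general statement. SAP 12.1.1 tests subjects with at least one event, and a subject who stops because of an AE is already a case. Step 5 shows that any-AE incidence does not move under such stopping.

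A reader might also take MR13A9-3 as evidence of dose-dependent stopping. Protocol 1.3.2.2 reports: "Study treatment was discontinued or interrupted due to 1 event in 1 subject in the 0.25" μg/kg group, then 2, 1 and 10 subjects at 0.5, 1.0 and 1.5 μg/kg. The contrast comes from 10/23 at 1.5 μg/kg, which is not studied here. The studied doses show 1/21, 2/21 and 1/19 (4.8%, 9.5%, 5.3%), with interruption and discontinuation combined, over 2 weeks. Put into step 2 at q = 30%, these give shortfalls of only 0.8, 1.6 and 0.9 points. The 1.5 μg/kg group also had the highest crude adverse drug reaction incidence (19/23), so heavy stopping did not hide events there.

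A third tempting reading is that a true 10% excess in event rate could vanish: 1.10 × 0.88/0.97 = 1.00. That needs 20% against 5% stopping, all at Week 2, and it concerns event counts, for which no between-group test is planned. With stops spread evenly it becomes 1.10 × 0.92/0.98 = 1.03.

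Unequal exposure would also be visible. The SAP reports discontinuation by group with a Fisher test and reasons (7.2), number of doses (9.1), treatment duration (9.3) and events leading to interruption or discontinuation (12.1.2, with listings in 13). Observed incidence under actual use is itself a legitimate measure.

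All of this limits the size and reach of the point. What remains is that those tables show unequal exposure without adjusting for it, and that counts fall even when the AE causes the stop.

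**Conclusion.** The point holds in a limited form. Observation time depends on early stopping and no AE output allows for it. If stopping differs between groups, the group with more of it has understated event counts, later-onset terms and incidence among subjects who stop before any AE. The any-AE incidence and its Fisher test are not lowered by stops that an AE causes.

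The likely size is modest: about 1 to 2 points at 5 to 10% stopping and about 3 points at 20%. It would be larger at higher incidence, and smaller if stops are spread out or AEs come early. These figures rest on assumed stopping rates and incidence, because the documents give neither. Dose-dependent stopping at 0.25 to 1.0 μg/kg is possible but is not shown. This is a cheap improvement to a stated safety objective and does not invalidate the crude tables.

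**What to change.** Keep the crude tables. In SAP 12.1.1, for any AE, any adverse drug reaction and special-interest events, add by group:

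- total events, and subjects with a first event, per 100 subject-weeks at risk, with the rate difference from placebo and 95% CI (for total events, an interval that allows for repeated events within a subject);
- both rates for each window already in SAP 12.1. Time to the end of follow-up includes off-drug weeks: 2 of 4 for a Week-2 stopper, 2 of 10 for a completer. The treatment-period rate avoids that dilution;
- Kaplan-Meier cumulative incidence at Day 57, from first dose to first event, censored at the end of AE collection.

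Reconcile the start of follow-up after discontinuation, since it sets the end of time at risk. Protocol 4.3.2 counts from the day after the discontinuation assessments. The footnotes to Protocol Table 13.5.1-2 and SAP Table 10.1-2 count from the day after the date of discontinuation, which 4.3.2 defines as the day of the decision.

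Cost: SAP wording and a few tables. AE onset dates (Protocol 9.12.1) and dosing days (Protocol 9.2) are already collected. Downside: the rates assume a roughly constant hazard, and the Kaplan-Meier figure assumes that censoring is unrelated to later risk, so each should be read beside the other and the crude figure.
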